7.3.1.4 Speech, Spatial, and Qualities of Hearing Scale (SSQ-12)

The short form of Speech, Spatial, and Qualities of Hearing questionnaire (SSQ-12)⁵ from MRC Institute of Hearing Research, UK, is a scaled-down version of the 49-item SSQ questionnaire. It is designed to compile a sub-set of items from the longer original 49-item version to represent the scale as a whole, measuring self-reported auditory disability, reflecting the reality of hearing in the everyday world.

Categories of assessment include:

- Hearing speech in a variety of competing contexts.
- The directional, distance and movement components of spatial hearing.
- Segregation of sounds and attending to simultaneous speech streams.
- Ease of listening.
- The naturalness, clarity, and identifiability of different speakers, different musical pieces and instruments, and different everyday sounds.

The SSQ-12 will be completed in the everyday listening condition at Visit 1 and Visit 5.

7.3.1.5 Patient Reported Questionnaire

The Patient Reported Questionnaire is an in-house developed questionnaire designed to collect subjective ratings on each subject's experiences with their current technology. The Patient Reported Questionnaire will be completed in the everyday listening condition at Visit

1 and Visit 5.

7.3.1.6 Medical History

Medical history CRFs will be collected at Visit 1. Information collected will include current or past medical or surgical conditions relevant to the conduct of the study.

7.3.1.7 Hearing History

Hearing history will be collected at Visit 1. Information collected will include duration, type and etiology of hearing loss in addition to any non-surgical hearing loss treatment details (e.g. hearing aid use).

7.3.2 Methods

7.3.2.1 Screening and Informed Consent

Subjects who have been deemed appropriate candidates for implantation according to standard clinical practice will be considered potential research subjects for this study. Informed consent must occur prior to study related activities with the exception of an audiogram performed within 90 days of Screening/Candidacy. Individuals will be appropriately counselled on the risks and benefits of study participation prior to participating in any study related activity. The risks of surgery shall be explained to the subjects as outlined in the Informed Consent Form. After reviewing the Informed Consent Form, the candidate will be given the opportunity to review and ask questions about the Informed Consent Form and/or the study prior to signing the Informed Consent Form. The candidates will be offered the opportunity to take the form home to discuss with family members should they choose to do so. If the participant agrees to participate, a copy of the executed informed consent will be provided to the participant. All individuals who provide informed consent will be assigned a unique identifier. A unique alphanumeric code will identify each subject throughout the course of the study.

7.3.2.2 Screening Visit

Subjects are consented into the study and the following data should be collected on all subjects who meet eligibility criteria. The only required documentation for subjects who do not meet eligibility criteria at the Screening visit is the Informed Consent Form and Eligibility electronic Case Report Form.

7.3.2.2.1 Electronic Case Report Forms

- Inclusion/Exclusion – Eligibility
- Demographics
- Hearing history
- Medical history
- Device History

7.3.2.2.2 Audiometric testing

Testing in each ear will include the following:

- Unaided air conduction thresholds: 250, 500, 1000, 2000, 3000, 4000, 6000, 8000 Hz with appropriate masking as required
- Unaided bone conduction thresholds: 250, 500, 1000, 2000, 3000, 4000 Hz with appropriate masking as required

7.3.2.3 Visit 1

7.3.2.3.1 Electronic Case Report Forms

- Concomitant Medications - See section 7.2.4 below for additional information.
- **7.3.2.3.2 Sound field hearing thresholds – 500, 1000, 2000, 4000 and 6000 Hz**
- Unaided
- Aided with Baha 5 Power on a Sound Arc.

Note: The test shall be performed with the non-test ear plugged/muffed.

7.3.2.3.3 CNC Word Test (Speech perception testing in quiet) – 2 lists 60dB(A) in sound field - S0

- Unaided
- Aided with Baha 5 Power on a Sound Arc

Note: The test shall be performed with the non-test ear plugged/muffed.

7.3.2.3.4 AzBio Sentence Test in Noise – 1 list 65 dB(A) +5dB SNR in sound field – S0N0

- Unaided
- Aided with Baha 5 Power on a Sound Arc

Note: The test shall be performed with the non-test ear plugged/muffed.

7.3.2.3.5 QuickSin Test – 4 lists 65 dB(A) in sound field – S0N180

- Unaided
- Aided with Baha 5 Power on a Sound Arc

Note: The test shall be performed with the non-test ear plugged/muffed.

7.3.2.3.6 Patient Reported Outcomes

- SSQ-12
- Patient Reported Questionnaire

7.3.2.4 Visit 2: Surgery

Subjects will be implanted with a commercially cleared Osia 2 system according to the surgical technique detailed in the Physicians Guide. Surgery is considered treatment, and thus the start of adverse event reporting.

7.3.2.5 Visit 3: 2 Week Post Surgery

Subjects will be seen for a 2-week post-surgical follow up to ensure the incision and implant site are healing appropriately in preparation for fitting at 4 weeks post- surgery. If applicable, device or procedure related adverse events and device deficiencies will be collected during this visit.

7.3.2.6 Visit 4: 4 Week Post Surgery

7.3.2.6.1 Fitting

- Optimization of the Osia 2 Sound Processor and device counselling

7.3.2.6.2 Sound field hearing thresholds – 500, 1000, 2000, 4000 and 6000Hz

- Aided with Osia 2 Sound Processor

Note: The test shall be performed with the non-test ear plugged/muffed.

7.3.2.6.3 CNC Word Test (Speech perception testing in quiet) – 2 lists 60dB(A) in sound field - S0

- Aided with Osia 2 Sound Processor

Note: The test shall be performed with the non-test ear plugged/muffed.

7.3.2.6.4 QuickSin Test – 4 lists 65 dB(A) in sound field – S0N180

- Aided with Osia 2 Sound Processor

Note: The test shall be performed with the non-test ear plugged/muffed.

7.3.2.7 Visit 5: 3 Months Post Surgery

7.3.2.7.1 Sound field hearing thresholds – 500, 1000, 2000, 4000 and 6000 Hz

- Unaided
- Aided with Osia 2 Sound Processor

Note: The test shall be performed with the non-test ear plugged/muffed.

7.3.2.7.2 CNC Word Test (Speech perception testing in quiet) – 2 lists 60dB(A) in sound field - S0

- Unaided
- Aided with Osia 2 Sound Processor

Note: The test shall be performed with the non-test ear plugged/muffed.

7.3.2.7.3 AzBio Sentence Test in Noise – 1 list 65 dB(A) +5dB SNR in sound field – S0N0

- Unaided
- Aided with Osia 2 Sound Processor

Note: The test shall be performed with the non-test ear plugged/muffed.

7.3.2.7.4 QuickSin Test – 4 lists 65 dB(A) in sound field – S0N180

- Unaided
- Aided with Osia 2 Sound Processor

Note: The test shall be performed with the non-test ear plugged/muffed.

7.3.2.7.5 Patient Reported Outcomes

- SSQ-12
- Patient Reported Questionnaire

7.3.2.8 Visit 6: 6 Months Post Surgery, End of Study

7.3.2.8.1 Sound field hearing thresholds – 500, 1000, 2000, 4000 and 6000Hz

- Aided with Osia 2 Sound Processor

Note: The test shall be performed with the non-test ear plugged/muffed.

7.3.2.8.2 CNC Word Test (Speech perception testing in quiet) – 2 lists 60dB(A) in sound field - S0

- Aided with Osia 2 Sound Processor

Note: The test shall be performed with the non-test ear plugged/muffed.

7.3.2.8.3 QuickSin Test – 4 lists 65 dB(A) in sound field – S0N180

- Aided with Osia 2 Sound Processor

Note: The test shall be performed with the non-test ear plugged/muffed

7.3.3 Safety Evaluations and Procedures

The identified risks and anticipated device related adverse events detailed in Sections 8 and 11 of the CIP will be assessed in the clinical investigation via reporting of all device and procedure related AEs/ADEs. Reporting timeframe will start for each individual subject at the time of treatment and end at either subject withdraw or completion in the study.

Safety data adjudication may be conducted by the Sponsor's Medical Officer in accordance with the Sponsor's standard operating procedures.

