7.2.5 Enrollment & Study Duration

The following subject status definitions apply:

Consented: A subject who has provided informed consent and is being assessed for eligibility according to the Screening requirements.

Screen Fail: A consented subject that has been determined to not meet all eligibility criteria for enrolment.

Enrolled/Treated: Subjects who have met all eligibility criteria, have qualified for surgery and have received the Osia 2 implant.

Withdrawn: Enrolled subjects who withdraw or are withdrawn by the Investigator or Sponsor before their expected end of study visits. Withdrawn subjects may still continue in safety follow-up until their scheduled end of study visit for reasons described in section 7.2.6.

The enrollment period for the clinical investigation is anticipated to be 6 - 8 months from the time of first subject consent to enrollment of the last subject.

The expected duration of each subject's participation is 7-8 months.

During this time there will be required research related visits.

- Screening
- Visit 1
- Visit 2: Surgery - Treatment
- Visit 3: 2-week check post-surgery
- Visit 4: 4-week post-surgery fitting
- Visit 5: 3 Months post-surgery
- Visit 6: 6 Months post-surgery (End of Study)

The anticipated total duration of the clinical investigation is therefore 12 - 18 months including set up, execution and closure. The execution phase of the Clinical Investigation is considered complete after the last subject, last visit. IRBs should remain open through closeout monitoring activities, until Sponsor notifies site of database lock.

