7.2.6 Criteria for Subject Withdrawal

Subjects can decide to withdraw from the investigation at any time. The Investigator shall ask the reason(s). The reason for withdrawal should be documented in the subject's source files and the case report form (CRF).

The Investigator or Sponsor may also decide to withdraw a subject from the clinical investigation if it is considered to be in their best interests.

Subject withdrawal may be for any of the following reasons:

- Adverse Event (AE)

- Device Deficiency (DD)
- CIP or GCP deviation
- Subject lost to follow-up
- Subject withdrew consent
- Subject death
- Sponsor decision
- Investigator decision
- Other (specify)

If subject withdrawal is due to problems related to the AMDT or comparator safety or performance, the Investigator shall ask for the subject's permission to continue in safety follow up (i.e., adverse events) until their scheduled End-of-Study visit.

If a subject is lost to follow-up, every possible effort must be made by the study site personnel to contact the subject and determine the reason for discontinuation. At least 3 separate attempts taken to contact the subject may be documented in the medical chart.

Treated subjects who are withdrawn/discontinued will not be replaced.

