11.2 Recording and Handling of Adverse Events

Subjects shall be carefully monitored during the clinical investigation and the investigator should inquire about AEs at investigation visits.

All ADEs, SAEs and UADEs associated with the AMDT will be recorded from the time of treatment with the AMDT through each individuals' last study visit. Ongoing ADEs, SADEs or UADEs at the time of study completion will be transitioned to ongoing clinical management.

It is recommended that source notes indicate the evaluation for AEs, even if none to report. All required device or procedure related AEs will be reported if observed, even if anticipated and/or acknowledged as a risk factor in the consent.

All required AEs will have the following information documented: start and stop dates, action taken, outcome, severity and investigators opinion on the potential relationship to the AMDT and study procedures. If an AE changes in severity, the most severe (highest) grade will be captured for that event on the Adverse Events CRF.

Events that include the typical stages of wound healing without additional medical intervention beyond the standard of care are not required to be reported for adverse device or procedure events.

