6.6.2 Secondary Endpoint

The secondary objective is to evaluate the safety of the Osia 2 system in a group of adult newly implanted recipients. Descriptive statistics specifically counts and percentages of device or procedure related adverse events will be summarized for the subject population.

The secondary endpoint will be assessed in the ITT analysis cohort with data through 6 months post-surgery.

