6.8 Safety Analyses

Adverse events will be collected prospectively following implantation according to the Clinical Investigation Plan *A post-market interventional cohort study evaluating the clinical efficacy of the Osia 2 system in the US Market*. Descriptive statistics specifically counts and percentages of device or procedure related AEs will be summarized. Any subjects who die, are treatment failures, or discontinued an intervention due to an adverse event will be summarized separately.

Adverse events (AE) will be reported for the ITT population. AEs will be tabulated with the number of events and subjects with event for each event type and overall. Rates will be reported as the number of subjects who experience at least one event during the analysis interval out of the total number of subjects with follow-up to the beginning of the analysis interval. Serious adverse events (SAEs) and will also be tabulated.

Device and procedure related AEs and SAEs, Adverse Device Effects (ADEs) and Serious Adverse Device Effects (SADEs), will also be summarized as described above. Unanticipated ADEs and SADEs (UADEs and USADEs) and adverse events leading to death or study discontinuation will be provided in listing format.

All device deficiencies will be reported in listing format.

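### Protocol 7.3.3 stops adverse event reporting at withdrawal, 7.2.6 continues it for some withdrawn subjects, and later related events can be missing from the 6-month incidence

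*Protocol*

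**What the plan says.** Four places in the protocol bear on when adverse event collection ends for one subject.

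- Section 7.3.3: collection starts at treatment and is to "end at either subject withdraw or completion in the study".
- Section 7.2.5: "Withdrawn subjects may still continue in safety follow-up until their scheduled end of study visit for reasons described in section 7.2.6".
- Section 7.2.6: if the subject withdraws because of a safety or performance problem with the test device or comparator, the investigator must ask permission for the subject to "continue in safety follow up (i.e., adverse events) until their scheduled End-of-Study visit". Withdrawal for other reasons carries no such request.
- Section 11.2: events are recorded from treatment "through each individuals' last study visit".

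The sole secondary endpoint (Protocol 9.2.2) is the incidence of device- or procedure-related adverse events. SAP 6.6.2 states: "The secondary endpoint will be assessed in the ITT analysis cohort with data through 6 months post-surgery". SAP 6.2 defines that cohort as all implanted subjects. SAP 6.8 takes the number of subjects with at least one event in an interval, "out of the total number of subjects with follow-up to the beginning of the analysis interval".

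**The concern.** Sections 7.3.3 and 7.2.6 give different answers for the same subject. Someone who leaves because of a device problem and agrees to safety follow-up is still under observation by 7.2.6, yet outside the reporting period by 7.3.3. Nothing says which section prevails, so sites could collect different data on comparable subjects.

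There is also a gap. The withdrawal reasons listed in 7.2.6 include a protocol deviation, a sponsor or investigator decision, and an open category. A subject who leaves for one of these may still carry the implant, but no section has the investigator ask for continued adverse event follow-up.

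In either case the subject has entered the SAP 6.8 denominator, and an event that was never collected cannot enter the numerator. The analysis then treats that subject as event-free for the rest of the interval. With 20 subjects, one such case is visible in the reported rate.

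**Working it through.** The documents state no adverse event rate, so there is no planned figure to reproduce. The check compares the rules and then bounds the effect.

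**The rules by type of withdrawal**

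| Subject | 7.3.3 | 7.2.5 / 7.2.6 | 11.2 |
|---|---|---|---|
| Withdraws over a device or comparator problem and agrees to follow-up | stops at withdrawal | continues to scheduled final visit | depends on whether a safety contact is a study visit |
| Withdraws over such a problem and declines | stops | stops | stops |
| Withdraws for another reason | stops | no request required | stops at last visit attended |

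The first row is the contradiction. The third is the gap.

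**How a missed event reaches the rate**

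1. Numerator: subjects with at least one recorded event in the interval (SAP 6.8).
2. Denominator: subjects followed to the start of the interval (SAP 6.8). A subject who leaves during the interval stays in it.
3. The SAP details multiple imputation only for the primary endpoint (6.6.1.2), and SAP 6.3 otherwise makes no attempt to impute. No censoring or time-at-risk method is given for adverse events.

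**Size.** Inputs from the documents: N = 20 (Protocol 7.2.3, an upper limit) and attrition up to 20% (Protocol 9.4), which is 0.20 × 20 = 4 subjects. That allowance was made for the sample size calculation and is borrowed here. Let k be the number of withdrawn subjects whose first related event comes after withdrawal and is not recorded. Taking the whole 6 months as one interval, the shortfall is k/20:

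- k = 1: 1/20 = 5 points
- k = 4: 4/20 = 20 points, reached only if every withdrawn subject is affected

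Assume, for illustration, that 2 subjects have recorded events. The report then shows 2/20 = 10% (Clopper-Pearson 95% interval 1.2% to 31.7%). With full follow-up it would show:

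| k | Rate | 95% interval |
|---|---|---|
| 1 | 3/20 = 15% | 3.2% to 37.9% |
| 2 | 4/20 = 20% | 5.7% to 43.7% |
| 3 | 5/20 = 25% | 8.7% to 49.1% |
| 4 | 6/20 = 30% | 11.9% to 54.3% |

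**A milder scenario.** Assume a true 6-month incidence of 30%, constant hazard, and 4 subjects leaving at times spread uniformly over 6 months for reasons unrelated to risk. Then λ = −ln(0.7)/6 per month. The mean probability of an event before leaving is 1 − 0.3/(−ln 0.7) = 1 − 0.3/0.3567 = 0.159. The expected reported rate is (16 × 0.30 + 4 × 0.159)/20 = 0.272, or 27.2%. The shortfall of 2.8 points is less than one subject in 20.

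**The case against.** The strongest reply is that the sections can be read together, with 7.3.3 as the general rule and 7.2.6 as a specific exception. The request in 7.2.6 is obligatory, it targets the subjects most likely to have later device events, and no text bars those events from the analysis. This has force: the loss depends on a site applying 7.3.3 literally or on the subject falling outside 7.2.6. But 7.3.3 neither mentions an exception nor refers to 7.2.6, so the reading has to be supplied by the site.

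Four stronger readings are tempting, and the documents do not support them.

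- That 7.2.5 and 7.2.6 continue follow-up for every withdrawn subject. Section 7.2.5 only permits it and points to 7.2.6, which requires permission and covers only device or comparator problems.
- That 11.2 is a third conflicting stopping rule. Its last study visit can be the scheduled final visit of a subject in safety follow-up; it is merely not decisive.
- That subjects leaving because of a related adverse event pull the overall percentage down. They already count as having at least one event, so a later revision or explant does not change their contribution to it.
- That all time after withdrawal is counted as event-free. A withdrawn subject drops out of the denominator of later intervals, so this holds only within the interval of withdrawal. The SAP does not define the intervals.

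It is also fair to say that SAP 6.4 already reports numbers followed at each visit and early exits by reason, and that death, loss to follow-up or withdrawn consent will often rule out further contact whatever the protocol says.

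**Conclusion.** The inconsistency between 7.3.3 and 7.2.6 is real, as is the gap for withdrawals outside 7.2.6. Related events after withdrawal can go unrecorded; the documents do not show that they will.

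If they do, the 6-month incidence is biased downward by 5 points per affected subject at N = 20, and by 20 points in the assumed worst case. These figures rest on one 6-month interval and on an assumed number of late first events; only N and the attrition allowance come from the documents. The overall percentage is affected only through subjects with no earlier related event, such as those leaving for poor performance, a device deficiency or a reason unconnected with the device. For the rest, the loss falls on event counts and on the rates by event type that SAP 6.8 also calls for.

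The primary endpoint is untouched, and Protocol 9.3.2 sets no hypothesis for the secondary one. The point therefore ranks below an essential correction, but it concerns one of the study's two objectives and bears on which data are collected.

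**What to change.** - Reconcile Protocol 7.2.5, 7.2.6, 7.3.3 and 11.2 to one end point for collecting related adverse events and device deficiencies: the scheduled 6-month date, for every implanted subject who agrees to continued safety contact.
- Extend the permission request in 7.2.6 to every withdrawal reason, keeping the subject's right to refuse.
- State in SAP 6.6.2 and 6.8 that events collected after withdrawal count in the 6-month numerator.

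The cost is a wording change in four protocol sections and two SAP sections, plus a phone or chart contact for about 4 subjects at the planned attrition. A Kaplan-Meier estimate censoring at last safety contact would be a reasonable addition but is optional. No new table of numbers followed is needed, since SAP 6.4 provides it.

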7.3.4 Concomitant Medication and Therapies

A comprehensive list of concomitant prescription medications will be captured in subjects who meet eligibility at the screening visit. Medications available over the counter will not be collected. Changes to concomitant prescription medications associated with device or procedure related adverse events will also be captured throughout the course of the trial.

7.4 Equipment Used for Evaluation of Performance and Safety

The following equipment will be used to evaluate performance and safety:

- Audiometers: data collected on this equipment will be used for candidacy determination and screening as well as postoperative assessments.

- Sound booth: location where a subject will be assessed. The sound booth will be outfitted with two speakers.
- Calibration records should include audiometer, insert earphones and/or headphones and sound field environment.

No other equipment calibration records will be required for this clinical investigation.

7.5 Sponsor Role in Conduct of the Clinical Investigation

Sponsor representatives may be present for intraoperative surgical support and clinical support of programming visits.

Sponsor representatives will be actively engaged in monitoring and operational communications with clinical sites for appropriate oversight and to ensure compliance. Further details regarding site communications and roles/responsibilities are documented in the Safety Data Handling Plan and Communications Plan.

To mitigate any potential bias, if it is requested that the Sponsor enter data into the electronic data capture system, the assigned individuals will not be involved in analysis of data. The Clinical Project Manager as well as the Clinical Review Board will be tasked with reviewing data listings for any abnormal trends associated with protocol compliance and/or safety issues. Formal analyses will be performed according to the Statistical Analysis Plan.

8 RISKS AND BENEFITS OF THE CLINICAL INVESTIGATION AND APPROVED MEDICAL DEVICE ON TEST

